3.5 Secondary endpoints/outcomes

Maternal

- Pregnancy outcomes from Visit 1 up to 6 weeks after delivery. These include live birth with congenital anomalies, miscarriage, fetal death/still birth (antepartum or intrapartum), mode of delivery, elective/therapeutic termination.
- Occurrence of serious adverse events (SAEs), AEs leading to study withdrawal, and MAAEs from Visit 1 (Day 0) up to 6 weeks / 6 months after delivery

- AEFI from Visit 1 up to 6 weeks after delivery. These include but are not limited to maternal death, hypertensive disorders of pregnancy (gestational hypertension, pre-eclampsia, pre-eclampsia with severe features including eclampsia), antenatal bleeding (morbidly adherent placenta, placental abruption, caesarean scar pregnancy, uterine rupture), postpartum haemorrhage, fetal growth restriction, gestational diabetes mellitus, non-reassuring fetal status, pathways to preterm birth (premature preterm rupture of membranes, preterm labour, iatrogenic preterm birth), chorioamnionitis, oligohydramnios, polyhydramnios, gestational liver disease (intrahepatic cholestasis of pregnancy, acute fatty liver of pregnancy), maternal sepsis.
- SARS-COV-2 IgG-specific antibody concentrations, (and neutralizing antibody titres and cellular immune responses in subsets) measured on blood samples collected from vaccinated maternal subjects at Day 0 (before vaccination), Day 28-42, Day 56-84, Day 84-112, Day 112-140, at delivery, between 4 weeks and 12 weeks, and at 12 months after delivery

Infant

- From birth through 6 weeks after birth, occurrences of SAEs, AEs leading to study withdrawal, and MAAEs
- Occurrence of neonatal AEs of special interest (up to 6 weeks after birth). These include but are not limited to small for gestational age, low birth weight including very low birth weight, neonatal encephalopathy, congenital microcephaly (postnatally or prenatally diagnosed), congenital anomalies (major external structural defects, internal structural defects, functional defects), neonatal death (in a preterm live birth or in a term live birth), neonatal infections (blood stream infections, meningitis, respiratory infection), respiratory distress in the neonate, preterm birth, failure to thrive, large for gestational age, macrosomia
- Developmental status at 12 months of age
- SARS-COV-2 IgG-specific antibody concentration, (and neutralizing antibody titres in a subset) against SARS-COV-2 measured on the cord blood sample collected at delivery, or on a blood sample collected from the infant within 3 days after birth (if no cord blood sample can be obtained)
- The ratio between cord blood and maternal SARS-COV-2 IgG-specific antibody concentrations or an infant blood sample collected within 72 hours after birth (if no cord blood sample can be obtained)
- SARS-COV-2 IgG-specific antibody concentrations and Neutralizing antibody titres against SARS-COV-2 in infants born to vaccinated mothers at Day 28 to 42 or Day 70 to 84 post-delivery.

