	
 To evaluate the reactogenicity of COVID-19 vaccines, when given as 1- or 2-dose vaccination regimens, in pregnant participants. 	
 Occurrence of solicited local and general adverse events (AE) that occur during a 7-day follow-up period after each vaccination (i.e., the day of vaccination and 6 subsequent days) Occurrence of unsolicited AEs that occur during a 30-day follow-up period after vaccination (i.e., the day of vaccination and 29 subsequent days)
Secondary (maternal)	
 To describe pregnancy outcomes in women who receive COVID-19 vaccine(s) during pregnancy. 	
 Pregnancy outcomes from Visit 1 up to 6 weeks after delivery. These include live birth with congenital anomalies, miscarriage, fetal death/stillbirth (antepartum or intrapartum), mode of delivery, elective/therapeutic termination.
	
 To evaluate safety in terms of SAEs and medically attended adverse events (MAAEs) in women who receive COVID-19 vaccine(s) during pregnancy. 	
 Occurrence of serious adverse events (SAEs), AEs leading to study withdrawal, and MAAEs from Visit 1 (Day 0) up to 6 weeks after delivery
	
 To evaluate safety in terms of AESI (including potential immune-mediated medical conditions (PIMMCs)) relevant to COVID-19, including possible vaccine-enhanced disease, in all women at any time after the first dose of a COVID-19 vaccine 	
 AESI from Visit 1 up to 6 weeks after delivery. These include but are not limited to maternal death, hypertensive disorders of pregnancy (gestational hypertension, pre-eclampsia, pre-eclampsia with severe features including eclampsia), antenatal bleeding (morbidly adherent placenta, placental abruption, caesarean scar pregnancy, uterine rupture), postpartum haemorrhage, fetal growth restriction, gestational diabetes mellitus, non-reassuring fetal status, pathways to preterm birth (premature preterm rupture of membranes, preterm labour, iatrogenic preterm birth), chorioamnionitis, oligohydramnios,

		polyhydramnios, gestational liver disease (intrahepatic cholestasis of pregnancy, acute fatty liver of pregnancy), maternal sepsis.

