2.1 Assessment and management of risk

This study involves vaccinating pregnant women with COVID-19 vaccines within a time period in the UK. There is a small risk of adverse reaction to any vaccine, but this risk is low and is no higher in this study than in routine practice. All staff administering vaccines in this study will be appropriately trained in vaccine administration and in managing any side effects from this and all vaccines will be given in an environment where emergency equipment is available.

This trial is categorised as:

- Type A = No higher than the risk of standard medical care

In the context of the current global pandemic of COVID-19 it is important that measures are taken to protect participants and staff from infection. All participating institutions should have an SOP or risk assessment for the conduct of study visits during this period and this must be available before visits recommence. If at any point a participant or a household contact of a participant is found to be experiencing any symptoms of COVID-19, the visit should not take place and they should be advised to follow the national public health guidance.

Benefit-risk assessment for trial participants in the Oxford/AstraZeneca cohort of Preg-CoV

This issue applies only to those pregnant women who have had one dose of the Oxford / Astra Zeneca (AZ) COVID-19 vaccine previously, with no serious side effects. For these individuals only, the benefits and risks of a second dose of the AZ COVID-19 vaccine will be discussed.

It is recognised that there is an increased risk of thromboembolic events with low platelets after a first (or unknown) doses of the AZ COVID-19 vaccine, with an overall incidence of 13.6 per million doses. No specific risk factors for this adverse event have been identified to this time. The incidence following a 2nd dose is reported to be 1.3 per million doses, with all cases reported being over the age of 50 years (MHRA Yellow Card reporting as of 26 May 2021).

Although pregnancy itself is associated with an increased risk of thrombosis, there is no evidence to suggest that pregnancy itself is a specific risk factor for the thromboembolic events described above. It should be acknowledged however, that there are very little data on the use of the AZ COVID-19 vaccine in pregnancy.

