3.2 Secondary objectives

Maternal

- To describe pregnancy outcomes in women who receive COVID-19 vaccine(s) during pregnancy.
- To evaluate safety in terms of SAEs and medically attended adverse events (MAAEs) in women who receive COVID-19 vaccines during pregnancy.
- To evaluate safety in terms of AESI (including potential immune-mediated medical conditions (PIMMCs)) relevant to COVID-19, including possible vaccine-enhanced disease, in all women at any time after the first dose of a COVID-19 vaccine.
- To evaluate the immunogenicity of COVID-19 vaccines, when given as 1- or 2-dose vaccination regimens, in serologically negative (to SARS-CoV-2) pregnant participants.
- To evaluate the immunogenicity of COVID-19 vaccines, when given as 1- or 2-dose vaccination regimens, in pregnant participants (regardless of serostatus as baseline).

Infant

- To evaluate the safety of infants born to women vaccinated with COVID-19 vaccine(s) up to 12 months after birth.
- To evaluate the transfer of SARS-CoV-2 specific antibodies from mothers vaccinated with COVID-19 vaccine(s), according to different regimens, to their infants at the time of delivery
- To evaluate the kinetics of SARS-CoV-2 specific maternal antibodies in infants born to mothers vaccinated with COVID-19 vaccine(s), up to 3 months after birth
- To assess the effect of gestational age at vaccination, interval between vaccination and delivery, maternal age, health status, vaccine type and schedule on immune responses and duration of immune responses in vaccinated women and on placental transfer and antibody kinetics in their infants

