
 • To evaluate safety in terms of AEFI (including potential immune-mediated medical conditions (PIMMCs)) relevant to COVID-19, including possible vaccine-enhanced disease, in all women at any time after the first dose of a COVID-19 vaccine. 	
 • AEFI from Visit 1 up to 6 weeks after delivery (Day 42 post-delivery). These include but are not limited to maternal death, hypertensive disorders of pregnancy (gestational hypertension, pre-eclampsia, pre-eclampsia with severe features including eclampsia), antenatal bleeding (morbidly adherent placenta, placental abruption, caesarean scar pregnancy, uterine rupture), postpartum haemorrhage, fetal growth restriction, gestational diabetes mellitus, non-reassuring fetal status, pathways to preterm birth (premature preterm rupture of membranes, preterm labour, provider-initiated preterm birth), chorioamnionitis, oligohydramnios, polyhydramnios, gestational liver disease (intrahepatic cholestasis of pregnancy, acute fatty liver of pregnancy), maternal sepsis. 	
Notification of AEFI to site by participant from enrolment to 6 weeks after delivery for the mother and up to 6 weeks after birth for the infant.

 • To evaluate the immunogenicity of COVID-19 vaccines, when given as 1- or 2-dose vaccination regimens, in serologically negative (to SARS-CoV-2) pregnant participants. 	
 • SARS-CoV-2 IgG-specific antibody concentrations, (and neutralizing antibody titres and cellular immune responses in subsets) measured on blood samples collected from vaccinated maternal subjects at Day 0 (before vaccination), Day 28-42, Day 56-84, Day 84-112, Day 112-140, at delivery, between 4 weeks and 12 weeks, and at 12 months after delivery 	
Maternal blood sampling at Day 0 (before vaccination), Day 28-42, Day 56-84, Day 84-112, Day112-140, at delivery, between 4 weeks and 12 weeks, and at 12 months after delivery

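### The maternal AESI endpoint closes 6 weeks after delivery, although its objective has no end date and AESI checks continue to 12 months

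*Protocol*

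**What the plan says.** **Objective.** Section 3.2 of the protocol reads: "To evaluate safety in terms of AESI (including potential immune-mediated medical conditions (PIMMCs)) relevant to COVID-19", and continues: "including possible vaccine-enhanced disease, in all women at any time after the first dose of a COVID-19 vaccine". The trial summary and section 3.7 carry the same objective.

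**Endpoint.** There are three versions, all with the same closing point:
- Trial summary: "AESI from Visit 1 up to 6 weeks after delivery".
- Section 3.5: the window is "AEFI from Visit 1 up to 6 weeks after delivery", and with the start of its open list the text reads "AEFI from Visit 1 up to 6 weeks after delivery. These include but are not limited to maternal death, hypertensive disorders of pregnancy". The list continues with further obstetric complications and ends with maternal sepsis.
- Section 3.7: "AEFI from Visit 1 up to 6 weeks after delivery (Day 42 post-delivery". The timepoint column also limits participant notification for the mother to enrolment through 6 weeks after delivery.

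**Data collection.** Section 7 and the schedules in Appendix 4 include an AESI check at visit 11 (182 days after delivery) and visit 12 (364 days after delivery). The trial summary sets maternal follow-up at 12 months after delivery.

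**Label.** The trial summary and section 3.2 use AESI. Section 3.5 uses AEFI, and section 3.7 uses AEFI in both the objective and the endpoint. Neither term is in the list of abbreviations or the definitions in section 9.1.

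**The concern.** The objective sets no end date after the first dose, whereas the endpoint meant to answer it has a firm one. Between day 43 and day 364 after delivery the protocol asks sites to look for AESIs, yet the endpoint does not count what they find. An AESI rate reported against this objective would describe pregnancy and the first 6 weeks after it, while the objective's wording would lead a reader to take it as covering all time after dose 1.

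The gap matters most for the two event types that the objective singles out. The obstetric events belong to pregnancy and the weeks around delivery, so a 6-week close suits them. Nothing in the protocol ties immune-mediated conditions or vaccine-enhanced disease to that period, and the objective says expressly that they are of interest at any time. Cohort 3 is the most exposed, because its second dose is given after delivery and so starts close to the cut-off.

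Two lesser points add to this. None of the events named in the endpoint is an immune-mediated condition or enhanced disease, so the objective's own categories have to be inferred from the open list. The AESI/AEFI switch also leaves it unclear whether one event class or two is meant.

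**Working it through.** The protocol gives no figure for this point, so there is none to reproduce. The check compares the windows and then measures the gap.

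**1. Windows side by side**

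| Item | Source | Start | End |
|---|---|---|---|
| Objective | 3.2, summary, 3.7 | first dose | none stated |
| Endpoint | summary, 3.5, 3.7 | visit 1 | 6 weeks (day 42) after delivery |
| Maternal notification | 3.7 | enrolment | 6 weeks after delivery |
| AESI checks | section 7, Appendix 4 | visit 2 (visit 1 in cohort 4) | visit 12 (day 364 after delivery) |

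The endpoint and the notification period agree with each other. Neither agrees with the objective or with the scheduled checks.

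**2. Post-delivery time outside the endpoint**

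364 − 42 = 322 days; 322/364 = 88%.

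**3. Share of all follow-up after dose 1**

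The endpoint also covers the time before delivery, so the post-delivery share alone overstates the loss. Let G be gestation at delivery and E gestation at dose 1, both in weeks.

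- Endpoint weeks = (G − E) + 6
- Follow-up weeks = (G − E) + 52

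E comes from the cohort windows in Tables 1 to 3. The protocol does not give G. Taking G = 40 as an assumption:

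| E (weeks) | Endpoint weeks | Follow-up weeks | Share |
|---|---|---|---|
| 13 | 33 | 79 | 42% |
| 24 | 22 | 68 | 32% |
| 28 | 18 | 64 | 28% |
| 34 | 12 | 58 | 21% |

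Varying G from 37 to 42 weeks, the share runs from 16% (G = 37, E = 34: 9/55) to 43% (G = 42, E = 13: 35/81).

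**4. Cohort 3 after the second dose**

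Visit 8, where cohort 3 receives its second dose, falls 0 to 7 days after delivery. The days left in the window are 42 − 0 = 42 down to 42 − 7 = 35.

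Table 3 also states an interval of 4 to 12 weeks. At its outer limit, with dose 1 at 34+0 and delivery at 40+0 (assumption), the second dose falls (34 + 12 − 40) × 7 = 42 days after delivery, the day the window closes. This is an extreme case, since Table 3 asks for the dose as soon as possible after delivery.

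**5. Event list**

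The named events are maternal death, pregnancy and delivery complications, and maternal sepsis. The list of events with case definitions in section 9.3 is likewise obstetric, fetal or neonatal. Neither names an immune-mediated condition or vaccine-enhanced disease. The endpoint list is, however, introduced as non-exhaustive in all three versions.

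**The case against.** **The list is open.** A reader might infer that the endpoint is purely obstetric and so cannot answer the objective at all. The documents do not support that. Every version says the list is not exhaustive, and the objective itself defines the class to include immune-mediated conditions and possible enhanced disease. Such an event arising within the window counts. A detailed AESI term list may also sit in a statistical analysis plan or study plan that is not shown. This objection stands for the list but does not reach the window, which is explicit in all three places.

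**Nothing is lost to safety oversight.** A reader might also infer that an event not named in the list may never reach the DSMB. The text gives no basis for this. DSMB review is triggered by SAEs or AESIs judged related to study interventions and is tied neither to the listed examples nor to a 6-week limit. Section 9.3 collects SAEs for the duration of the study and maternal medically attended events at any time, and section 10.3.3 presents all SAEs and unsolicited AEs. This objection stands. The point concerns what the endpoint counts, not whether events are seen.

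**Other endpoints cover the later period.** This holds only in part. In the summary and section 3.7 the maternal SAE and medically attended event endpoint also closes at 6 weeks, and section 3.5 gives 6 weeks / 6 months. COVID-19 occurrence runs to 12 months, but it is exploratory and counts occurrence, not enhanced disease.

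**The thrombosis event.** Section 2.1 discusses thrombosis with low platelets after the AstraZeneca vaccine, and its absence from the list might look like a serious gap. For second doses that section gives 1.3 per million, with all reported cases over 50 years of age; eligibility stops at 45. Even if all 100 women in cohort 4 received that vaccine, 100 × 1.3/1,000,000 = 0.00013 events would be expected. Naming it is optional.

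**Conclusion.** The point holds as a mismatch in time, with a secondary weakness in naming and labelling. The objective runs without limit after the first dose, while the endpoint and the notification period stop 6 weeks after delivery. AESIs found at visits 11 and 12 are therefore collected but fall outside the endpoint.

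The size is 322 of 364 post-delivery days excluded. Counting time before delivery as well, the window covers 21% to 42% of follow-up after dose 1, assuming delivery at 40 weeks, and 16% to 43% over 37 to 42 weeks. A cohort 3 second dose at visit 8 has 35 to 42 days inside the window.

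The conclusion rests on reading the endpoint wording as governing which events are counted. It does not show that the endpoint fails within its window or that any safety signal would go unreviewed. It concerns a secondary, descriptive safety objective and does not affect the primary analysis or the sample size. It should still be corrected, because it decides which events count towards a stated objective.

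**What to change.** - In the trial summary and sections 3.5 and 3.7, split the endpoint window. For the objective's non-obstetric AESIs (immune-mediated conditions and possible vaccine-enhanced disease, both named), count events from first dose through visit 12. Keep 6 weeks after delivery for the obstetric list.
- In section 3.7, extend the maternal notification period to match.
- In sections 3.5 and 3.7, replace AEFI with AESI. The trial summary and section 3.2 already use it.

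The cost is wording only. The AESI checks at visits 11 and 12 are already scheduled, so no visit is added and the sample size does not change.

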3.6 Exploratory endpoints/outcomes

Maternal

- Levels of maternal IgA and/or other IgG (and subtypes) against SARS-CoV-2 in colostrum and breast milk within 3 days and 14 days where possible
- Occurrence of COVID-19 up to 12 months post-delivery
- SARS-COV-2 IgG-specific antibody concentrations, (and neutralizing antibody titres and cellular immune responses in subsets) measured on blood samples collected from vaccinated maternal subjects at Day 0 (before booster vaccination), Day 28-42, Day 56-84, Day 84-112, Day 112-140, at delivery, between 4 weeks and 12 weeks, and at 12 months after delivery
- SARS-COV-2 IgG-specific antibody concentrations, (and neutralizing antibody titres and cellular immune responses in subsets) measured on blood samples collected from vaccinated maternal subjects at Day 0 (before vaccination), Day 28-42, Day 56-84, Day 84-112, Day 112-140, at delivery, between 4 weeks and 12 weeks, and at 12 months after delivery

Infant

- Occurrence of COVID-19 up to 12 months post-delivery (infant)

3.7 Table of endpoints/outcomes

Objectives	Outcome Measures	Timepoint(s) of evaluation of this outcome measure (if applicable)

Primary (maternal)
 
 To determine whether the immune response, in COVID-19 seronegative participants, to immunisation with COVID-19 vaccines according to “long” dosing intervals is superior to that observed following immunisation according to “short” dosing intervals. 	
 SARS-COV-2 IgG-specific antibody concentrations measured on blood samples collected from vaccinated maternal subjects at delivery. 	
Maternal blood sampling at delivery

 To evaluate the reactogenicity of COVID-19 vaccines, when given as 1- or 2-dose vaccination regimens, in pregnant participants. 	
 Occurrence of solicited local and general adverse events (AE) that occur during a 7-day follow-up period after each vaccination (i.e., the day of vaccination and 6 subsequent days) 	
Diary data entry (solicited AE) from Day 0 to Day 6.

	
 Occurrence of unsolicited AEs that occur during a 30-day follow-up period after vaccination (i.e., the day of vaccination and 29 subsequent days) 	
Diary data entry (unsolicited AE) from Day 0 to Day 29.

Secondary Objectives Maternal
 
 To describe pregnancy outcomes in women who receive COVID-19 vaccine(s) during pregnancy. 	
 Pregnancy outcomes from Visit 1 up to 6 weeks after delivery. These include live birth with congenital anomalies, miscarriage, fetal death/still birth (antepartum or intrapartum), mode of delivery, elective/therapeutic termination. 	
Review at delivery and at 3 days, 14 days, and 42-48 days after delivery.

 To evaluate safety in terms of SAEs and medically attended adverse events (MAAEs) in women who receive COVID-19 vaccines during pregnancy. 	
 Occurrence of serious adverse events (SAEs), AEs leading to study withdrawal, and MAAEs from Visit 1 (Day 0) up to 6 weeks after delivery 	
Notification of SAE / AE / MAAE to site by participant from enrolment to 1 year after delivery / birth.


 • To evaluate safety in terms of AEFI (including potential immune-mediated medical conditions (PIMMCs)) relevant to COVID-19, including possible vaccine-enhanced disease, in all women at any time after the first dose of a COVID-19 vaccine. 	
 • AEFI from Visit 1 up to 6 weeks after delivery (Day 42 post-delivery). These include but are not limited to maternal death, hypertensive disorders of pregnancy (gestational hypertension, pre-eclampsia, pre-eclampsia with severe features including eclampsia), antenatal bleeding (morbidly adherent placenta, placental abruption, caesarean scar pregnancy, uterine rupture), postpartum haemorrhage, fetal growth restriction, gestational diabetes mellitus, non-reassuring fetal status, pathways to preterm birth (premature preterm rupture of membranes, preterm labour, provider-initiated preterm birth), chorioamnionitis, oligohydramnios, polyhydramnios, gestational liver disease (intrahepatic cholestasis of pregnancy, acute fatty liver of pregnancy), maternal sepsis. 	
Notification of AEFI to site by participant from enrolment to 6 weeks after delivery for the mother and up to 6 weeks after birth for the infant.

 • To evaluate the immunogenicity of COVID-19 vaccines, when given as 1- or 2-dose vaccination regimens, in serologically negative (to SARS-CoV-2) pregnant participants. 	
 • SARS-CoV-2 IgG-specific antibody concentrations, (and neutralizing antibody titres and cellular immune responses in subsets) measured on blood samples collected from vaccinated maternal subjects at Day 0 (before vaccination), Day 28-42, Day 56-84, Day 84-112, Day 112-140, at delivery, between 4 weeks and 12 weeks, and at 12 months after delivery 	
Maternal blood sampling at Day 0 (before vaccination), Day 28-42, Day 56-84, Day 84-112, Day112-140, at delivery, between 4 weeks and 12 weeks, and at 12 months after delivery


 To evaluate the immunogenicity of COVID-19 vaccines, when given as 1- or 2-dose vaccination regimens, in pregnant participants (regardless of serostatus as baseline). 	
 SARS-COV-2 IgG-specific antibody concentrations, (and neutralizing antibody titres and cellular immune responses in subsets) measured on blood samples collected from vaccinated maternal subjects at Day 0 (before vaccination), Day 28-42, Day 56-84, Day 84-112, Day 112-140, at delivery, between 4 weeks and 12 weeks, and at 12 months after delivery 	
Maternal blood sampling at Day 0 (before vaccination), Day 28-42, Day 56-84, Day 84-112, Day 112-140, at delivery, between 4 weeks and 12 weeks, and at 12 months after delivery

Secondary Objectives
 
Infant
 
 To evaluate the safety of infants born to women vaccinated with COVID-19 vaccine(s) up to 12 months after birth. 	
 From birth through 6 weeks after birth, occurrences of SAEs, AEs leading to study withdrawal, and MAAEs. 	
Review of SAEs, AEs leading to study withdrawal, and MAAEs at delivery and at 3 days, 14 days, and 42-48 days after delivery, and at 6 months and 12 months.

	
 Occurrence of neonatal AEs of special interest (up to 6 weeks after birth). These include but are not limited to small for gestational age, low birth weight including very low birth weight, neonatal encephalopathy, congenital microcephaly (postnatally or prenatally diagnosed), congenital anomalies (major external structural defects, internal structural defects, functional defects), neonatal death (in a preterm live birth or in a term live birth), neonatal infections (blood stream infections, meningitis, respiratory infection), respiratory distress in the neonate, preterm birth, failure to thrive, large for gestational age, macrosomia 	
Review of neonatal AESIs at delivery and at 3 days, 14 days, and 42-48 days after delivery, and at 6 months and 12 months.

	
 Developmental status at 12 months of age 	
Perform neurodevelopmental assessment at 12 months of age


 To evaluate the transfer of SARS-CoV-2 specific antibodies from mothers vaccinated with COVID-19 vaccines, according to different regimens, to their infants at the time of delivery 	
 SARS-COV-2 IgG-specific antibody concentration, (and neutralizing antibody titres in a subset) against SARS-COV-2 measured on the cord blood sample collected at delivery, or on a blood sample collected from the infant within 3 days after birth (if no cord blood sample can be obtained) 	
Cord blood sample taken at delivery or infant blood sample taken within 3 days of life (if no cord blood sample can be obtained).

	
 The ratio between cord blood and maternal SARS-COV-2 IgG-specific antibody concentrations or an infant blood sample collected within 72 hours after birth (if no cord blood sample can be obtained) 	

 To evaluate the kinetics of SARS-CoV-2 specific maternal antibodies in infants born to mothers vaccinated with COVID-19 vaccine(s), up to 3 months after birth 	
 SARS-COV-2 IgG-specific antibody concentrations and Neutralizing antibody titres against SARS-COV-2 in infants born to vaccinated mothers at Day 28 to 42 or Day 70 to 84 post- delivery 	
Infant blood sampling between day 42 and day 84 post-delivery

 To assess the effect of gestational age at vaccination, interval between vaccination and delivery, maternal age, health status, vaccine type and schedule on immune responses and duration of immune responses in vaccinated women and on placental transfer and antibody kinetics in their infants 	
 SARS-COV-2 IgG-specific antibody concentration, (and neutralizing antibody titres in a subset) against SARS-COV-2 measured on the cord blood sample collected at delivery, or on a blood sample collected from the infant within 3 days after birth (if no cord blood sample can be obtained) The ratio between cord blood and maternal SARS-COV-2 IgG-specific antibody concentrations or an infant blood sample collected within 72 hours after birth (if no cord blood sample can be obtained) 	
Maternal blood sample taken at delivery and cord blood sample taken at delivery or infant blood sample taken within 3 days of life (if no cord blood sample can be obtained).

	
 SARS-COV-2 IgG-specific antibody concentrations and Neutralizing antibody titres against SARS-COV-2 in infants born to vaccinated mothers at Day 28 to 42 or Day 70 to 84 post- delivery 	

Exploratory Objectives
 
Maternal
 
 • To describe SARS-COV-2 antibodies in breast milk of mothers who receive COVID-19 vaccine in pregnancy 	
 • Levels of maternal IgA and/or IgG (and subtypes) against SARS-CoV-2 in colostrum and breast milk within 3 days and 14 days where possible 	
Collection of colostrum and breast milk sample at 3 days and 14 days post-delivery.

 • To describe the effectiveness of COVID-19 vaccines in pregnancy against maternal COVID-19 in pregnancy or post-partum 	
 • Occurrence of COVID-19 up to 12 months post-delivery (mother) 	
Identification and laboratory confirmation of SARS-CoV-2 infection and symptomatic COVID-19 throughout the study.

 • To evaluate the immunogenicity of a COVID-19 vaccine when given as a booster dose, in pregnant participants who have received one dose of a COVID-19 vaccine before pregnancy 	
 • SARS-COV-2 IgG-specific antibody concentrations, (and neutralizing antibody titres and cellular immune responses in subsets) measured on blood samples collected from vaccinated maternal subjects at Day 0 (before booster vaccination), Day 28-42, Day 56-84, Day 84-112, Day 112-140, at delivery, between 4 weeks and 12 weeks, and at 12 months after delivery 	
Maternal blood sampling at Day 0 (before vaccination), Day 28-42, Day 56-84, Day 84-112, Day 112-140, at delivery, between 4 weeks and 12 weeks, and at 12 months after delivery


 • To compare the immunogenicity of a COVID-19 vaccine, when given as a booster dose to pregnant participants of 28-34 weeks' gestation who have received a prime dose of a COVID-19 vaccine before pregnancy, with the immunogenicity of a COVID-19 vaccine when given as a prime dose to pregnant participants of 28-34 weeks' gestation who have not received a dose of a COVID-19 vaccine previously 	
 • SARS-COV-2 IgG-specific antibody concentrations, (and neutralizing antibody titres and cellular immune responses in subsets) measured on blood samples collected from vaccinated maternal subjects at Day 0 (before vaccination), Day 28-42, Day 56-84, Day 84-112, Day 112-140, at delivery, between 4 weeks and 12 weeks, and at 12 months after delivery 	
Maternal blood sampling at Day 0 (before vaccination), Day 28-42, Day 56-84, Day 84-112, Day 112-140, at delivery, between 4 weeks and 12 weeks, and at 12 months after delivery

 • To assess the impact of prime-boost interval on immunogenicity when a booster dose is given to pregnant participants of 28-34 weeks' gestation who have received a prime dose of COVID-19 vaccine before pregnancy 	
 • SARS-COV-2 IgG-specific antibody concentrations, (and neutralizing antibody titres and cellular immune responses in subsets) measured on blood samples collected from vaccinated maternal subjects at Day 0 (before vaccination), Day 28-42, Day 56-84, Day 84-112, Day 112-140, at delivery, 	
Maternal blood sampling at Day 0 (before vaccination), Day 28-42, Day 56-84, Day 84-112, Day 112-140, at delivery, between 4 weeks and 12 weeks, and at 12 months after delivery

	between 4 weeks and 12 weeks, and at 12 months after delivery	
Exploratory Objectives Infant 
 To describe the effectiveness of maternal antibodies against SARS-CoV-2 to protect against COVID-19 / symptomatic disease / severity in infants in the first 12 months of life 	
 Occurrence of COVID-19 up to 12 months post-delivery (infant) 	Identification and laboratory confirmation of SARS-CoV-2 infection and symptomatic COVID-19 throughout the study.

 To describe the effectiveness of breast milk antibodies against SARS-CoV-2 to protect against COVID-19 / symptomatic disease / severity in infants in the first 12 months of life 	
 Occurrence of COVID-19 up to 12 months post-delivery (infant) 	Identification and laboratory confirmation of SARS-CoV-2 infection and symptomatic COVID-19 throughout the study.

